## 1. INTRODUCTION

[figure not shown]
The purpose of this SAP is to describe the planned analyses to be included in the CSR for Study 214144. Details of the final analyses are provided.

### 1.1. Objectives, Estimands and Endpoints

Objectives	Endpoints
Primary	

 
To assess the consistency of therapeutic response of gepotidacin at the Test of cure (TOC) Visit (Day 10 to 13) in female participants with acute uncomplicated cystitis with qualifying bacterial uropathogen(s) at Baseline that all are susceptible to nitrofurantoin in Japan, with that from global studies (Studies 204989 and 212390).
 
	
 
Therapeutic response (combined per-participant microbiological and clinical response) at the TOC Visit
 

Secondary	

 
To assess the therapeutic response of gepotidacin compared to nitrofurantoin as an active reference descriptively, at the TOC Visit, in female participants with acute uncomplicated cystitis with qualifying bacterial uropathogen(s) at Baseline that all are susceptible to nitrofurantoin
 
	
 
Therapeutic response at the TOC Visit
 

 
To assess the clinical efficacy and microbiological efficacy of gepotidacin at the TOC Visit in female participants with acute uncomplicated cystitis with qualifying bacterial uropathogen(s) at Baseline that all are susceptible to nitrofurantoin
 
	
 
Clinical outcome and response at the TOC Visit
 
Microbiological outcome and response at the TOC Visit
 

 
To assess the therapeutic response, clinical efficacy and microbiological efficacy of gepotidacin at the TOC Visit in female participants with acute uncomplicated cystitis who have qualifying uropathogen(s) resistant to two or more specific classes of antimicrobials at Baseline
 
	
 
Therapeutic response at the TOC Visit
 
Clinical outcome and response at the TOC Visit
 
Microbiological outcome and response at the TOC Visit
 

 
To assess the clinical efficacy of gepotidacin at the TOC Visit in female participants with acute uncomplicated cystitis
 
	
 
Investigator assessment of clinical response at the TOC Visit
 


 
To assess the safety and tolerability of gepotidacin in female participants with acute uncomplicated cystitis
 
	
 
Occurrence of treatment-emergent adverse events (AEs), serious AEs (SAEs) and adverse events of special interest (AESIs)
 
Change from baseline in clinical laboratory tests
 
Change from baseline in electrocardiograms (ECGs)
 
Change from baseline in vital sign measurements
 

 
To determine the plasma and urine PK concentrations of gepotidacin in female participants with acute uncomplicated cystitis
 
	
 
Gepotidacin plasma and urine concentrations
 

Objectives	Endpoints
Exploratory	

CCI

### Primary estimand

The primary clinical question of interest is: Whether the therapeutic response at the TOC visit in female participants with acute uncomplicated cystitis who have qualified uropathogen(s) at Baseline that all are susceptible to nitrofurantoin in this study is consistent with that from the global studies, regardless of intervention discontinuation for any reason. Receipt of systemic antimicrobials will impact the endpoint definition (see Section 6.2.1.1 and Section 6.2.1.2).

The estimand is described by the following attributes:

- Population: Japanese and non-Japanese (from Studies 204989 and 212390) female participants with acute uncomplicated cystitis who have qualifying uropathogen(s) at Baseline that all are susceptible to nitrofurantoin.
- Treatment condition: Gepotidacin 1500 mg BID for 5 days in this study versus gepotidacin 1500 mg BID for 5 days in the global studies (Studies 204989 and 212390) regardless of adherence.

- Variable: Therapeutic response (combined per-participant microbiological and clinical response) at the TOC Visit (the detailed definitions are provided in Section 6.2.1). Microbiological success is defined as eradication (i.e., reduction) of all qualifying bacterial uropathogens recovered at baseline to  $<10^3$  colony-forming units/mL (CFU/mL) as observed on quantitative urine culture without the participant receiving other systemic antimicrobials. Clinical success is defined as resolution of signs and symptoms of acute cystitis present at Baseline (and no new signs and symptoms) without the participant receiving other systemic antimicrobials.
- Summary measure: Comparison of the proportion of Japanese participants achieving therapeutic success in this study with 10th percentile of the predicted distribution for the proportion of participants achieving therapeutic success in this study derived from the global studies (Studies 204989 and 212390)
- Intercurrent events (ICEs):
  - Study treatment discontinuation (due to any reason) – treatment policy strategy (interest is in the treatment effect regardless of study treatment discontinuation)
  - Use of systemic antimicrobials – composite strategy. This ICE is captured through the definitions of microbiological and clinical response (see Section 6.2.1.1 and Section 6.2.1.2)

#### **Rationale for estimand:**

Interest in this study lies in whether the efficacy of gepotidacin treatment in this study is consistent with the global studies.

The clinical question of interest in this study and the global studies (Studies 204989 and 212390) lies in the treatment effect of gepotidacin regardless of whether the full course of 5 days of treatment was taken or not, which reflects how patients may be treated in clinical practice. Hence, a treatment policy strategy is appropriate for treatment withdrawal before completing 5 days of treatment. Use of other systemic antimicrobials may confound the bacterial culture results; thus, the microbiological response will be considered failure. For clinical data, the use of a systemic antimicrobial for acute uncomplicated cystitis is a sign of treatment failure and use of a systemic antimicrobial for another infection cannot be considered a success as it confounds the assessment of efficacy. Therefore, the definition of a successful therapeutic response precludes the use of other systemic antimicrobials.

Secondary estimands are provided in Section 4.3.

## 1.2. Study Design

Overview of Study Design and Key Features	

Female adolescent or adult participants with suspected acute cystitis based on clinical signs and symptoms and nitrite or pyuria (<math>>15</math> WBC/HPF or the presence of 3+/large leukocyte esterasea) from a pretreatment clean-catch midstream urine sample
	
Baseline (Day 1) Visit
 
3:1 Randomization stratified by age and acute cystitis recurrencea
 
Oral 1500 mg gepotidacin BID and matching nitrofurantoin placebob for 5 days
 
Oral 100 mg nitrofurantoin BID and matching gepotidacin placebob for 5 days
 
On-therapy Visit Days 2 to 4
 
Primary Efficacy TOC Visit Days 10 to 13
 
Follow-up Visit Days 28 ± 3

Design Features	
 
This is a Phase III randomized, multicentre, active reference, double-blind, double-dummy study in adolescent and adult Japanese female participants to evaluate the efficacy and safety of gepotidacin. The primary objective is to assess consistency of this study with global studies (Studies 204989 and 212390) for therapeutic response of gepotidacin.
 
The study duration will be approximately 28 days with 4 visits.
 
Participants will be stratified by age category (<math>\leq 50</math> years, or <math>>50</math> years) and acute uncomplicated cystitis recurrence (recurrent or nonrecurrent) and will be randomly assigned in a 3:1 ratio to receive either oral gepotidacin or oral nitrofurantoin (active reference).
 

Study intervention	
 
Gepotidacin: 1500 mg administered orally BID for 5 days
 
Nitrofurantoin: 100 mg administered orally BID for 5 days
 

Study intervention Assignment	Participants will be stratified by age category and acute uncomplicated cystitis recurrence (recurrent or nonrecurrent). Recurrence is defined as a confirmed infection [not including the current infection in the calculation] with at least 1 prior episode within the past 3 months, at least 2 prior episodes within the past 6 months, or at least 3 prior episodes within the past 12 months before study entry). Participants will be randomly assigned in a 3:1 ratio to receive either oral gepotidacin or oral nitrofurantoin.
Interim Analysis	No formal interim analysis will be planned. Blinded review for therapeutic, clinical, and microbiological response at the TOC visit may be conducted during the study.

## 2. STATISTICAL HYPOTHESES

The primary objective is to assess the “consistency” of therapeutic success rate between the gepotidacin arm in this Eagle-J study with the pooled gepotidacin arm in the two global studies (Studies 204989 and 212390). The observed proportion of participants in the gepotidacin arm at the TOC visit achieving therapeutic success in this study will be compared with the predictive distribution of the therapeutic success rate estimated from the two global studies (Studies 204989 and 212390). “Consistency” is defined as:

$$\hat{p}_a > \frac{r_{aj}^{(10\%)}}{n_{aj}}$$

, where:

$\hat{p}_a$ : Observed proportion of participants achieving therapeutic success on gepotidacin in this study

$n_{aj}$ : Number of participants in gepotidacin of this study

$r_{aj}^{(10\%)}$ : The lower 10th percentile of the cumulative distribution of the prior predictive distribution derived from the global study data for the expected number of participants achieving therapeutic success out of  $n_{aj}$  participants.

Therefore,  $\frac{r_{aj}^{(10\%)}}{n_{aj}}$  is the threshold response rate that needs to be observed to meet

therapeutic success, assuming the response rate is consistent with the global study response rate. The predictive distribution is defined as:

$$r_{aj} \sim \int \text{Binomial}(r_{aj} | n_{aj}, p_a) \times \text{Beta}(p_a | \alpha = r_{ag}, \beta = n_{ag} - r_{ag}) dp_a$$

, where:

$r_{aj}$ : The expected number of participants achieving therapeutic success in the gepotidacin arm of this study

$r_{ag}$ : The pooled number of participants achieving therapeutic success in the gepotidacin arm across both global studies.

$n_{ag}$ : The pooled number of participants in the gepotidacin arms across both global studies.

The two global studies (204989 and 212390) have almost the same study design and the therapeutic response would be similar as well. Therefore, the data will be simply pooled to derive the predictive distribution.

Example:

Assuming 884 participants on the gepotidacin arm and a 76% observed therapeutic response rate in the global studies, there is an approximately 10% probability of observing  $\leq 56$  out of 81 responders in this study if the true gepotidacin response rate in this study is consistent with the response rate estimated from the global studies.

Therefore, the success rule for gepotidacin is set to require a therapeutic response rate greater than 69.1% (56/81) in order to demonstrate consistency with global results in this example.

The secondary objective is to assess the difference between the therapeutic response of gepotidacin with the nitrofurantoin therapeutic response at the TOC Visit in Japanese female participants with acute uncomplicated cystitis with qualifying bacterial uropathogen(s) at Baseline that all are susceptible to nitrofurantoin. The difference in the therapeutic response rate between gepotidacin and nitrofurantoin will be assessed descriptively.

## 2.1. Multiplicity Adjustment

No multiplicity adjustment approaches will be used.

## 3. ANALYSIS SETS

Analysis Set	Definition / Criteria	Analyses Evaluated
Screened	
 
All participants who were screened for eligibility
 
	
 
Study Population
 

Intent-to-Treat (all participants) (ITT-ALL)	
 
All participants who were randomly assigned to study treatment in the study.
 
Participants will be analyzed according to their randomized study treatment.
 
	
 
Listing
 

Intent-to-Treat (ITT)	
 
All participants in ITT-ALL population, except for participants from the site (Site ID: PPD [ ] ) due to GCP violation
 
Participants will be analyzed according to their randomized study treatment.
 
	
 
Study Population
 
Efficacy
 

Microbiological ITT (all participants) (micro-ITT-ALL)	
 
All participants randomly assigned to study treatment who receive at least 1 dose of study treatment and have a qualifying baseline uropathogen (defined in Section 6.2.10), from a quantitative bacteriological culture of a pretreatment clean-catch midstream urine specimen.
 
Participants will be analyzed according to their randomized study treatment.
 
Note that qualifying uropathogens include only the uropathogen species/groups [Gram-negative bacilli (e.g. E. coli, K. pneumoniae, P. mirabilis), S. saprophyticus, and Enterococcus spp.], defined in Section 6.2.10.
 
	
 
Listing
 

Microbiological ITT (micro-ITT)	
 
All participants in micro-ITT-ALL, except for participants from the site (Site ID: PPD [ ] ) due to GCP violation.
 
Participants will be analyzed according to their randomized study treatment.
 
	
 
Study Population
 
Efficacy
 

Micro-ITT NTF-S (all participants) (micro-ITT-ALL NTF-S)	
 
All participants in the micro-ITT-ALL Population whose baseline qualifying bacterial
 
	
 
Listing
 

Analysis Set	Definition / Criteria	Analyses Evaluated
	
uropathogens that all are susceptible to nitrofurantoin (NTF-S). Broth microdilution nitrofurantoin MIC result from JMI Laboratories (if available) will take precedence over global central laboratory (GCL) nitrofurantoin MIC result for determining susceptibility to nitrofurantoin.
 
 
• Nitrofurantoin susceptibility interpretations will be based on the Clinical and Laboratory Standards Institute (CLSI) guidelines
 
• Participants with missing MIC susceptibility results for any qualifying uropathogens will not be included in the NTF-S subpopulation.
 
• Participants will be analyzed according to their randomized study treatment.
 
	
Micro-ITT NTF-S	
 
• All participants in the micro-ITT Population whose baseline qualifying bacterial uropathogens that all are susceptible to nitrofurantoin (NTF-S). Broth microdilution nitrofurantoin MIC result from JMI Laboratories (if available) will take precedence over global central laboratory (GCL) nitrofurantoin MIC result for determining susceptibility to nitrofurantoin.
 
• Nitrofurantoin susceptibility interpretations will be based on the Clinical and Laboratory Standards Institute (CLSI) guidelines
 
• Participants with missing MIC susceptibility results for any qualifying uropathogens will not be included in the NTF-S subpopulation.
 
• Participants will be analyzed according to their randomized study treatment.
 
• Note that this population does not include the participants in the affected site by GCP violation (Site ID: PPD [REDACTED]).
 
	
 
• Study Population
 
• Efficacy
 

Analysis Set	Definition / Criteria	Analyses Evaluated
Micro-ITT NTF-S (Global Study)	
 
• All participants from the global studies (Studies 204989 and 212390) in the micro-ITT NTF-S (IA set) Population defined in individual studies, who are not enrolled into this study but into each of the global studies. See the individual RAP for the detailed definition of this analysis population.
 
• Note: this population will be referred as non-Japanese population.
 
• Participants will be analyzed according to their randomized study treatment.
 
	
 
• NA
 

Micro-ITT NTF-S (Entire)	
 
• All participants from micro-ITT NTF-S Population and micro-ITT NTF-S (Global Study) Population.
 
• This is the primary analysis population.
 
• Participants will be analyzed according to their randomized study treatment.
 
	
 
• Efficacy
 

Micro-ITT-ALL NTF-S (Entire)	
 
• All participants from micro-ITT-ALL NTF-S Population and micro-ITT NTF-S (Global Study) Population.
 
• Participants will be analyzed according to their randomized study treatment.
 
	
 
• Efficacy
 

Micro-ITT MDR	
 
• All participants in the micro-ITT Population who have any qualifying baseline bacterial uropathogens that are resistant to two or more classes of antimicrobials. See the detail for MDR definition in Section 6.2.11.
 
• Participants will be analyzed according to their randomized study treatment.
 
	
 
• Efficacy
 

Micro-ITT MDR (Global Study)	
 
• All participants from the global studies (Studies 204989 and 212390) in the micro-ITT Population who have any qualifying baseline bacterial uropathogens that are resistant to two or more classes of antimicrobials. See the detail for MDR definition in Section 6.2.11.
 
	
 
• Efficacy
 

Analysis Set	Definition / Criteria	Analyses Evaluated
	
 
Participants will be analyzed according to their randomized study treatment.
 
	
Micro-ITT MDR (Entire)	
 
All participants from micro-ITT MDR Population and micro-ITT MDR (Global Study) Population.
 
Participants will be analyzed according to their randomized study treatment.
 
	
 
Efficacy
 

Safety (all participants) (Safety-ALL)	
 
All randomized participants who receive at least 1 dose of study treatment.
 
Participants will be analyzed according to their actual treatment received.
 
Note: if a participant receives both gepotidacin and nitrofurantoin, they will be summarized within gepotidacin 1500 mg BID.
 
	
 
Safety
 

Safety	
 
All randomized participants in Safety-ALL population, except for the participants from the site (Site ID: PPD [REDACTED] ) due to GCP violation.
 
Note: if a participant receives both gepotidacin and nitrofurantoin, they will be summarized within gepotidacin 1500 mg BID.
 
Participants will be analyzed according to their actual study treatment received.
 
	
 
Safety
 

Pharmacokinetics (all participants) (PK-ALL)	
 
All randomized participants who receive at least 1 dose of study treatment and have at least 1 non-missing plasma or urine PK concentration (Non-quantifiable [NQ] values will be considered as non-missing values).
 
This population will be used in the assessment and characterization of plasma and urine concentrations (summary table). Note: if a participant receives both gepotidacin and nitrofurantoin, they will be listed only (i.e. not summarized within gepotidacin 1500 mg BID). Plasma and/or urine samples for participant randomized
 
	
 
Listing
 

Analysis Set	Definition / Criteria	Analyses Evaluated
	nitrofurantoin will not be measured.	
Pharmacokinetic (PK)	
 
All randomized participants in PK-ALL population, except for the participants from the site (Site ID: PPD ) due to GCP violation.
 
This population will be used in the assessment and characterization of plasma and urine concentrations (summary table). Note: if a participant receives both gepotidacin and nitrofurantoin, they will be listed only (i.e., not summarized within gepotidacin 1500 mg BID). Plasma and/or urine samples for participant randomized nitrofurantoin will not be measured.
 
	
 
PK
 

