9.2. Analysis Sets

For purposes of analysis, the following populations are defined:

Population	Description
Intent-to-Treat (ITT) Population	All participants randomly assigned to study treatment. Participants will be analyzed according to their randomized study treatment.
Microbiological ITT (micro-ITT) Population	All participants randomly assigned to study treatment who receive at least 1 dose of study treatment and have a qualifying baseline uropathogen (defined in 10.8), from a quantitative bacteriological culture of a pretreatment clean-catch midstream urine specimen. Participants will be analyzed according to their randomized study treatment.
Micro-ITT NTF-S Population	All participants in the micro-ITT Population whose baseline qualifying bacterial uropathogens all are susceptible to nitrofurantoin (NTF-S). Participants with missing MIC susceptibility results for any qualifying uropathogens will not be included in the NTF-S subpopulation. Participants will be analyzed according to their randomized study treatment.
Micro-ITT NTF-S (Global Study) Population	All participants from the global studies (Studies 204989 and 212390) in the micro-ITT NTF-S Population defined in individual studies, who are not enrolled into this study but into each of the global studies.

Population	Description
Micro-ITT NTF-S (Entire) Population	All participants from micro-ITT NTF-S Population and micro-ITT NTF-S Population (Global Study) Population. This is the primary analysis population.
Micro-ITT MDR Population	All participants in the micro-ITT Population who have any qualifying baseline bacterial uropathogens that are resistant to two or more classes of antimicrobials. Participants will be analyzed according to their randomized study treatment.
Pharmacokinetic (PK) Population	All randomized participants who receive at least 1 dose of study treatment and have at least 1 nonmissing plasma or urine PK concentration (Non-quantifiable [NQ] values will be considered as non-missing values). This population will be used in the assessment and characterization of plasma and urine concentrations (summary table).
Safety Population	All randomized participants who receive at least 1 dose of study treatment. Participants will be analyzed according to their actual treatment received.

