9.3.4. Safety Analysis

All safety analyses will be performed on the Safety Population. All reported AEs will be coded using MedDRA and summarized by system organ class and preferred terms.

The safety estimand will use a treatment policy strategy for the ICE of study treatment discontinuation, as safety will be assessed at all post-baseline assessments irrespective of whether the participant completed the treatment.

Treatment-emergent AE (TEAE) is defined if AE onset date/time is on or after treatment start date/time. The number and proportion of treatment-emergent AEs, study treatment-related AEs, deaths, SAEs, and AEs leading to study treatment or study withdrawal will be provided. Treatment-emergent AEs will be summarized by maximum intensity.

Adverse events of special interest will include CV, gastrointestinal, and *Clostridiooides difficile infection or colitis* events. In addition, AEs associated with acetylcholinesterase inhibition are also considered special interest. As described in the SAP, manual and programmatic reviews of AEs/preferred terms will be used to assess these events.

The severity of specified AEs and laboratory abnormalities will be graded according to the modified DMID toxicity grading system (Section 10.12). Data will be tabulated and reported by absolute grade for Grades 3 and higher, and shift tables, as appropriate.

Change from baseline over time in laboratory parameters, ECGs and vital signs will be summarized with descriptive statistics. The frequency of laboratory abnormality events along with the shift from baseline to the worst-case post-baseline value will be provided. Abnormal liver chemistry results will be determined using increases above the upper limit of normal.

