## 4.6. Safety Analyses

The safety analyses will be based on the Safety Analysis population, unless otherwise specified.

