#### 4.6.2. Adverse Events

An adverse event (AE) is considered treatment emergent if the AE onset date/time is on or after study intervention start date/time. If time is missing, only date will be compared. All AE and SAE summaries (including AESI) will be based on Treatment emergent adverse events unless otherwise specified.

Adverse events will be coded using the standard Medical Dictionary for Regulatory Affairs (MedDRA dictionary).

An overview summary of AEs, including counts and percentages of participants will be produced with:

- Any AE
- AE by maximum grade
- Study intervention related AEs
- AEs leading to withdrawal from study
- AEs leading to permanent discontinuation of study intervention
- AEs leading to permanent discontinuation of study intervention or withdrawal from study
- Study intervention related AEs leading to permanent discontinuation of study intervention
- SAEs
- Non-serious AEs
- Study intervention related SAE
- Fatal SAEs
- SAEs leading to permanent discontinuation of study intervention
- AEs of special interest (3 types of AESI will be provided separately)

In addition to overall summary, separate summaries of AE will be produced according to the below table. Note that missing grade of AE will be imputed as "Severe".

	Summary by PT	Summary by PT and SOC	Summary by PT, SOC and Maximum Grade
Any AEs		Y	Y
Study intervention related AEs		Y	Y
AEs leading to permanent discontinuation of study intervention		Y	Y
Common ( $\geq 1\%$ ) AEs	Y		
Serious AEs		Y	Y
Non-serious study intervention related AEs	Y		
Serious Fatal and Non-Fatal study intervention related AEs	Y		

Furthermore, the following summaries will be produced for disclosure purpose.

- Summary of Common ( $\geq 5\%$ ) non-serious Adverse Events by SOC and PT (Number of Subjects and Occurrences)
- Summary of SAEs by SOC and PT (Number of Subjects and Occurrences)

A study intervention-related AE is defined as an AE for which the investigator classifies the possible relationship to study intervention as “Yes”. A worst-case scenario approach will be taken to handle missing relatedness data, i.e., the summary table will include events with the relationship to study intervention as ‘Yes’ or missing.

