#### **4.6.2.5. Impact of GCP violation**

This analysis is based on Safety-ALL population. For transparency, the number and percentage of participants experiencing any adverse events will be presented by treatment arm, SOC and PT.

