#### **4.6.3.3. ECG**

The number of participants with worst case QTc values relative to potential clinical importance criteria which are post-baseline relative to baseline will be summarised. The summary will include baseline data and worst case post-baseline, and visits (i.e. On-Therapy and TOC visits). The baseline categories are: Low, within Range and High for PCI criteria. The change categories for PCI criteria are: To Low, To within Range or No Change, To High. The determination of worst case post-baseline takes into account both planned and unscheduled assessments. A summary of change from baseline in ECG values will be produced by visit.

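### With the GCP-violation site dropped from the Safety set, the all-dosed set gets one adverse event table and no serious-event, grade, AChE-I, QTc or liver summary

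*SAP*

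**What the plan says.** Protocol 9.2 defines the Safety Population as "All randomized participants who receive at least 1 dose of study treatment. Participants will be analyzed according to their actual treatment received". Protocol 9.3.4 adds: "All safety analyses will be performed on the Safety Population". Neither section removes a site.

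SAP Amendment 1 divides this into two sets. In SAP Section 3, Safety-ALL carries the protocol's definition, and Safety becomes "All randomized participants in Safety-ALL population, except for the participants from the site" where the GCP violation occurred. SAP 4.6 then sets the default: "The safety analyses will be based on the Safety Analysis population, unless otherwise specified". The one safety subsection that names Safety-ALL is 4.6.2.5, where "the number and percentage of participants experiencing any adverse events will be presented by treatment arm, SOC and PT".

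The version history states that populations were modified to exclude the affected participants. SAP 4.9 lists the change from the protocol as the addition of populations because of the violation.

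**The concern.** The participants at this site took study drug, and a GCP violation does not undo that exposure. The protocol treats QT prolongation, acetylcholinesterase inhibition and *C. difficile* as risks to follow (2.3.1) and predefines AESIs (8.3.7). For findings of this kind a single identifiable case can matter more than a rate.

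The SAP works the same way. Under 4.6.2.4, an event seen on gepotidacin but not on nitrofurantoin goes onto the short list of potential adverse reactions. QT prolongation, serious and severe events, and AESIs go on automatically. That screen names no population, so it runs on the reduced set. One serious event at the excluded site might never reach the qualitative review that the short list feeds.

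The site is also treated unevenly across domains. The primary efficacy analysis is repeated in full with the site included (SAP 4.2.3.5), and PK concentrations are listed with the affected participants in (4.3.8.2). Safety gets one table.

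**Working it through.** The plan states no figure on this point, so the check is mainly a tracing of outputs to analysis sets.

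**Step 1: which set is the default?** SAP 4.6 refers to a Safety Analysis population, a name that Section 3 does not use. It must mean Safety, because 4.6.1 names the Safety population and 4.6.2.5 has to name Safety-ALL as an exception. Section 3 tags Safety-ALL for safety use, but a tag assigns no output.

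**Step 2: what does each output show for the site?**

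| Output | SAP section | Safety-ALL version planned? | What remains visible for the site |
|---|---|---|---|
| Any AE by arm, SOC, PT | 4.6.2.5 | Yes | Counts by term |
| AE overview; SAE, fatal, related, discontinuation and maximum-grade summaries | 4.6.2 | No | The term only, without these attributes |
| SAE summary for disclosure | 4.6.2 | No | The term only, without the serious flag |
| GI, cardiovascular, *C. difficile* AESIs | 4.6.2.1, 6.2.2.1 | No | Terms visible; no maximum grade, and no per-participant count across the cardiovascular terms |
| AChE-I AESIs | 4.6.2.1 | No | Not derivable: needs onset within 12 hours of the latest dose |
| Potential adverse reaction screen | 4.6.2.4 | No | Nothing |
| Worst-case liver chemistry | 4.6.3.1 | No | Only what was reported as an AE |
| Worst-case QTc | 4.6.3.3 | No | Only what was reported as an AE |
| Listings of AEs, SAEs, death profiles | 4.6.2 | No set named | Unclear |

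For the disclosure row, SAP 4.6.2 says only that "the following summaries will be produced for disclosure purpose" and names no population, so the default applies. The ECG section likewise plans "The number of participants with worst case QTc values relative to potential clinical importance criteria" without naming one.

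**Step 3: how large could this be?** The number dosed at the site is not given, so this is an illustration under assumptions.

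- Planned randomization: about 300 at 3:1 (SAP 5.1.3), so 300 × 3/4 = 225 on gepotidacin, all taken as dosed.
- Assumed site size: 4 to 40 participants, also split 3:1.
- Assumed true incidence of the event on gepotidacin: 1%.
- Chance of at least one event among m participants: 1 − 0.99^m.

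| Assumed site size | Gepotidacin participants removed | Chance that they include at least one event | Gepotidacin participants left | Chance of seeing at least one event among those left |
|---|---|---|---|---|
| 0 | 0 | 0% | 225 | 89.6% |
| 4 | 3 | 3.0% | 222 | 89.3% |
| 12 | 9 | 8.6% | 216 | 88.6% |
| 20 | 15 | 14.0% | 210 | 87.9% |
| 40 | 30 | 26.0% | 195 | 85.9% |

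The ability to detect such an event at all changes little. What is lost is recognition of a particular serious or special-interest case at the site.

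**The case against.** The sponsor has a reasonable case, and several parts of it stand.

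- **Events are not erased.** A reader might infer that SAEs and AESIs at the site leave the safety summaries altogether. They do not. An SAE is an AE and is counted in the Safety-ALL table. SAP 6.2.2.1 defines *C. difficile* events by two preferred terms, GI events by a whole SOC and cardiovascular events by a list of terms, so all of these can be read from a table by SOC and PT.
- **Important QTc and liver findings should surface as AEs.** The protocol requires clinically significant ECG changes (7.1.2, 8.2.3) and laboratory changes (8.2.4) to be reported as AEs, and possible Hy's Law cases as SAEs (10.3.2). This narrows the gap but leaves part of it: a QTc above the 450 msec limit in SAP 6.2.3.1, or an ALT multiple counted in 4.6.3.1, reaches an AE table only if the investigator judged it significant.
- **Listings may cover the site.** ITT-ALL is tagged for listings in Section 3, and the AE, SAE and death listings name no set. That is an ambiguity to settle and does not show that the site is left out of them.
- **The exclusion is disclosed.** The version history states it, and the Safety-ALL table is offered for transparency. Nothing supports a reading that the change was concealed, although 4.9 does not spell out that the protocol's Safety Population became smaller.
- **Reliability is unknown.** The cause of the violation is redacted. If the site's records are doubtful, its grades and laboratory values may be too. That argues for labelled parallel tables and does not by itself justify leaving the serious and special-interest outputs out.

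A reader might also assume that some fixed percentage of serious events is missing. The documents give no site size. SAP 4.1.1 expects thin accrual per center, which if anything points to a small number.

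**Conclusion.** The point holds in a limited form. The SAP narrows the protocol's Safety Population, defaults safety outputs to the narrower set, and gives the all-dosed set one table. Events at the site remain countable by preferred term. No planned summary identifies them as serious, fatal, related or leading to discontinuation, gives their maximum grade, or classes them as AChE-I AESIs. Numeric QTc and liver results there have no summary, and the short-list screen and SAE disclosure table omit the site by default.

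No amount of bias or share of missing events can be claimed. The 3% to 26% range depends on the assumed site size, the 3:1 split at the site and the 1% incidence. The change is worth making because it is cheap and restores the protocol's own definition where single cases matter most.

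**What to change.** In SAP 4.6.2.5, add the following on Safety-ALL, each labelled and shown beside the site-excluded version:

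- the AE overview;
- SAEs and deaths;
- AEs leading to discontinuation;
- AESIs, including AChE-I, by maximum grade;
- the worst-case QTc and liver chemistry summaries;
- the potential adverse reaction screen of 4.6.2.4.

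Produce the SAE disclosure table on Safety-ALL, and name Safety-ALL as the population for the AE, SAE and death listings. In 4.9, state that the protocol's Safety Population was narrowed.

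The cost is reruns of existing outputs on a set that is already defined, with no new data or methods. The drawback is that some figures will come from a site whose data are in question, so the labels must make clear which version is which.
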